7.3 Analysis Windows

For parameters summarized by visit, an analysis window will be assigned to each nominal visit. Each assessment will be assigned to an analysis visit based on the analysis window in which the assessment date falls. Details are defined in [Appendix A](#).

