6.2.3 Premedication for Venetoclax

Venetoclax can cause rapid reduction in tumors and thus poses a risk for TLS in the initial **CCI** phase. Changes in blood chemistries consistent with TLS requiring prompt management can occur as early as 6 to 8 hours following the first dose of venetoclax and at each dose increase.

The risk of TLS is a continuum based on multiple factors, including tumor burden and comorbidities. Perform tumor burden assessments, including radiographic evaluation (e.g., computed tomography [CT] scan), assess blood chemistry (potassium, uric acid, phosphorus, calcium, and creatinine) in all subjects and correct pre-existing abnormalities prior to initiation of treatment with venetoclax. A repeat CT scan may be performed at Cycle 2, Day 21 (± 3 days) in subjects at high risk of TLS, at investigator's discretion. Reduced renal function ($\text{CrCl} < 80 \text{ mL/min}$) further increases the risk. The risk may decrease as tumor burden decreases [see VENCLEXTA™ prescribing information: Warnings and Precautions (5.1) and Use in Specific Populations (8.6)].

Table 3 below describes the recommended TLS prophylaxis and monitoring during venetoclax treatment based on tumor burden determination from clinical trial data. All subject co-morbidities should be considered before final determination of prophylaxis and monitoring schedule.

Table 3: Recommended Tumor Lysis Syndrome Prophylaxis for Venetoclax Based on Tumor Burden from Clinical Trial Data

Tumor Burden		Prophylaxis		Blood Chemistry Monitoring^{c,d}
		Hydration^a	Antihyperuricemics	Setting and Frequency of Assessments
Low	All LN <5 cm AND ALC <25 x 10 ⁹ /L	Oral (1.5 to 2 L)	Allopurinol ^b	Outpatient • Predose, 6 to 8 hours, 24 hours at first dose of CCI and CCI • Predose at subsequent ramp-up doses
Medium	Any LN 5 cm to <10 cm OR ALC ≥25 x 10 ⁹ /L	Oral (1.5 to 2 L) and consider additional intravenous	Allopurinol	Outpatient • Predose, 6 to 8 hours, 24 hours at first dose of CCI and CCI • Predose at subsequent ramp-up doses • Consider hospitalization for subjects with CrCl <80 mL/min at first dose of CCI and CCI see below for monitoring in hospital
High	Any LN ≥10 cm OR ALC ≥25 x 10 ⁹ /L AND any LN ≥5 cm	Oral (1.5 to 2 L) and intravenous (150 to 200 mL/hr as tolerated)	Allopurinol; consider rasburicase if baseline uric acid is elevated	In hospital at first dose of CCI and CCI • Predose, 4, 8, 12 and 24 hours Outpatient at subsequent ramp-up doses • Predose, 6 to 8 hours, 24 hours

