6.5 Phase 1b Dose Escalation Portion

[Figure 1](#) depicts the dose escalation schema Cohorts 1 and 2 of this study.

Figure 1: Phase 1b Dose Escalation Schema for Cohorts 1 and 2

As this combination has not previously been evaluated in a clinical trial, a toxicity assessment will occur after the first 6 subjects with relapsed/refractory CLL have been accrued to dose level 1. At this time, accrual will be held until all subjects are followed for 8 weeks (2 cycles). Toxicities will then be reviewed by the principal investigator. If, during this time, there is ≤ 1 DLT (outlined below), Phase 1b expansion will begin for Cohort 1. If more toxicity than expected is observed and there are 2 or more DLTs in this group, the next 3 to 6 subjects will be

accrued at [REDACTED] and this group will be monitored until all have completed [REDACTED] of therapy. If there are 2 or more DLTs in this group, 3 to 6 subjects will be accrued at [REDACTED]

[REDACTED] The highest dose level at which less than 2/6 subjects experience DLT will be the recommended Phase 1b expansion dose. Once the Phase 1b dose-escalation portion is complete for Cohort 1 and dose level is established, this cohort will open to full accrual and Cohort 2 will open enrollment for 6 subjects at the recommended Phase 1b expansion dose for Cohort 1. A safety analysis for Cohort 2 will be performed after the first 6 subjects are followed for at least 8 weeks (2 cycles). The Acerta Review Committee will discuss the data in conjunction with the principal investigator and, once safety is established in this cohort, Cohort 2 will open for full Phase 1b expansion.

Dose-limiting toxicity will be defined as the following toxicities related to protocol therapy during the first [REDACTED] of therapy:

- \geq Grade 3 nonhematologic toxicity lasting for \geq 7 days
- \geq Grade 3 prolongation of the QTc interval
- Grade 4 neutropenia (ANC <500/ μ L) lasting \geq 7 days after discontinuation of therapy without growth factors or lasting \geq 5 days after discontinuation of therapy while on growth factors in subjects with pre-treatment ANC \geq 1 \times 10⁹/L
- \geq Grade 3 febrile neutropenia
- Grade 4 thrombocytopenia (platelet count <20,000/ μ L) lasting \geq 7 days after discontinuation of therapy or requiring transfusion in subjects with pretreatment platelet count >50,000/ μ L.
- Dose delay due to toxicity for >14 consecutive days

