 - B. Response evaluations will be done every 12 weeks from randomization for the first 24 months (with the 4th evaluation shifted to Cycle 12 Day 1 rather than Cycle 13 Day 1, to align with study visits), and then every 24 weeks thereafter. Hematology results must be done within 7 days of CT scans. Bone marrow biopsies/aspirates to confirm a CR must be done within 4 weeks of the CT scan, which showed CR.
 - C. PB samples will be used to evaluate for MRD every 3 cycles (at the discretion of the investigator, in line with scheduled response assessments, per protocol).
 - D. Specific times and tube types for correlative samples are outlined in [Section 13.2](#).
 - E. PK analysis will be performed on the first 8 expansion group patients of Cohort 1. Schedule can be found in [Section 13.3](#).
 - F. If performed as part of relapse analysis
 - G. As outlined in [Section 13.4](#)
 - H. Visits to continue every 6 cycles thereafter (\pm 7 days).
 - I. A safety follow-up (SFU) visit is required for all subjects 30 days (+7) from the last dose of study drug.
 - J. After discontinuation of study treatment for any reason, each subject should be followed until disease progression or the start of alternative anticancer therapy. If disease progression has not occurred at the time of the 30-day SFU visit, discontinuation follow-up (DFU) visits should occur approximately every 12 weeks until disease progression. During this period, subjects will be followed via CT scans every 24 weeks; after 2 years in DFU, CT scans will be yearly. AE and concomitant medication reporting, irrespective of seriousness, ends 30 days after the last dose of study drug(s).
 - K. After disease progression or the start of alternative anticancer therapy, all subjects (unless they have withdrawn consent) will be contacted approximately every 12 weeks by telephone, to assess survival until death or lost to follow up.

Table 12: Schedule of Assessments – Cohort 3

Day	Screening	Treatment Phase & Response Evaluation												SFU	Discontinuation follow-up ¹	Relapse/ Disease Progression	Long-term follow-up	
		Cycle 1		Cycle 2			Cycle 3			Cycles 4 -7	Cycles 10, 13, 16, 19, 22	Cycle 24	Cycle 24 q6 cycles					
		1	15	1	8	15	22	1	8	15	22	1	1	1	1			
Study Windows (days)	-28	±3		±3				±3				±3	±3	±3	±7	+7	±7	±7
Study Drug Administration ¹		CCI																
Acalabrutinib																		
Rituximab																		
Venetoclax																		
Procedures																		

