15.0 APPENDICES

Appendix A: Analysis Windows

Tumor assessment/CT/SPD For Cohort 1 and 2				
			Analysis Window (Study Day)	
Nominal Visit	Study Day	Nominal Month	Lower (inclusive)	Upper (inclusive)
C4D1	85	0		127
C7D1	169	1	128	211
C10D1	253	1	212	281
C12D1	309	1	282	351
C15D1	393	13	352	435
C18D1	477	15	436	519
C21D1	561	18	520	603
C24D1	645	21	604	687
C30D1	813	27	688	855
C36D1	981	32	856	

Tumor assessment/CT/SPD For Cohort 3 and 4				
			Analysis Window (Study Day)	
Nominal Visit	Study Day	Nominal Month	Lower (inclusive)	Upper (inclusive)
C4D1	85	0		127
C7D1	169	1	128	211
C10D1	253	1	212	295
C13D1	337	1	296	379
C16D1	421	13	380	463
C19D1	505	15	464	547
C22D1	589	18	548	617
C24D1	645	21	618	687
C30D1	813	27	688	855
C36D1	981	32	856	

Hematology / Chemistry				
			Analysis Window (Study Day)	
Nominal Visit	Study Day	Nominal Month	Lower (inclusive)	Upper (inclusive)
C1D1	1	0		1
C1D8	8	1	2	12
C1D15	15	1	13	21
C2D1	29	1	22	43
C3D1	57	2	44	71
C4D1	85	2	72	99
C5D1	113	3	100	127
C6D1	141	4	128	155
C7D1	169	5	156	183
C8D1	197	6	184	211
C9D1	225	7	212	239
C10D1	253	8	240	267
C11D1	281	9	268	295
C12D1	309	10	296	351
C15D1	393	13	352	435

C18D1	477	15	436	519
C21D1	561	18	520	603
C24D1	645	21	604	687
C30D1	813	27	688	855
C36D1	981	32	856	

Physical Examination/ECOG				
			Analysis Window (Study Day)	
Nominal Visit	Study Day	Nominal Month	Lower (inclusive)	Upper (inclusive)
C1D1	1	0		1
C1D8	8	1	2	12
C1D15	15	1	13	21
C2D1	29	1	22	43
C3D1	57	2	44	71
C4D1	85	2	72	99
C5D1	113	3	100	127
C6D1	141	4	128	155
C7D1	169	5	156	183
C8D1	197	6	184	211
C9D1	225	7	212	239
C10D1	253	8	240	267
C11D1	281	9	268	295
C12D1	309	10	296	351
C15D1	393	13	352	435
C18D1	477	15	436	519
C21D1	561	18	520	603
C24D1	645	21	604	687
C30D1	813	27	688	855
C36D1	981	32	856	

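### SAP Appendix A leaves the C36D1 window open-ended and sets the two limits after C24D1 42 days too early, so visits after Cycle 36 and some off-schedule records get the wrong label in by-visit output

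*SAP*

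**What the plan says.** SAP Section 7.3 assigns labels purely by date: "Each assessment will be assigned to an analysis visit based on the analysis window in which the assessment date falls". The windows are in Appendix A, in four tables: tumor assessment for Cohorts 1 and 2, tumor assessment for Cohorts 3 and 4, hematology/chemistry, and physical examination/ECOG. The columns are visit, study day, nominal month, lower limit and upper limit. The last rows read "C24D1 645 21 604 687" (the lower limit is 618 in the Cohort 3/4 tumor table), "C30D1 813 27 688 855" and "C36D1 981 32 856". The final row has no upper limit in any of the four tables.

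On the visit calendar, Protocol Section 8, Table 11, footnote H says after Cycle 24: "Visits to continue every 6 cycles thereafter", with a tolerance of 7 days either way. Tables 12 and 13 give the same 6-cycle spacing for Cohorts 3 and 4, except that CT moves to every 12 cycles after Cycle 36. Protocol Section 6.7 places the end of study 36 cycles after the last subject is enrolled and expects follow-up past Cycle 36.

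**The concern.** A window table should send each record to the visit it belongs to, and it can do so only if the limits follow the visit spacing. Here the spacing doubles after Cycle 24, but the limits do not change with it, and the last window takes in everything that follows. By-visit output under C36D1 would then mix data from Cycle 36 with data from much later. It would also hold several records for each long-staying subject, with nothing to say which one is used. First record, last record and all records would give different tables, and a reader would take the column for a Cycle 36 result.

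**Working it through.** **Inputs.** The cycle-length text is blacked out. Protocol Section 6.5 equates 8 weeks with 2 cycles, so I take 28 days. Spacing after C24 is 6 x 28 = 168 days. Window limits are from Appendix A.

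**1. Target days.** Cycle n Day 1 = 28(n - 1) + 1. This gives C24D1 = 645, C30D1 = 813 and C36D1 = 981, and it reproduces every Day 1 target in Appendix A, which supports the 28-day reading.

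**2. Limits.** The natural limit is the midpoint between neighboring targets. Up to C24D1 the plan uses exactly that:
- Cohort 1/2 tumor table: 127, 211, 281, 351, 435, 519, 603.
- Cohort 3/4 tumor table: 127, 211, 295, 379, 463, 547, 617.
- Laboratory and physical-examination tables: every limit from C2D1 on.

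The pattern then breaks (Cohort 1/2 tumor table shown):

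| Visits | Target days | Midpoint | Stated upper limit | Difference |
|---|---|---|---|---|
| C21D1, C24D1 | 561, 645 | 603 | 603 | 0 |
| C24D1, C30D1 | 645, 813 | 729 | 687 | -42 |
| C30D1, C36D1 | 813, 981 | 897 | 855 | -42 |
| C36D1, C42D1 | 981, 1149 | 1065 | blank | none stated |

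Both misplaced limits equal target + 42 (645 + 42 = 687; 813 + 42 = 855). Forty-two days is half of the 84-day, 3-cycle spacing, so the earlier half-width appears to have been carried over. C30D1 now reaches 813 - 688 = 125 days back and 855 - 813 = 42 days forward.

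**3. Records affected by the limits.** Days 688-728 are nearer C24D1 but labelled C30D1. Days 856-896 are nearer C30D1 but labelled C36D1. Each band is 41 days (Days 729 and 897 are equidistant). For example, Day 700 is 55 days from C24D1 and 113 from C30D1, and is labelled C30D1.

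**4. On-schedule visits.** At target +/-7 days, C24 (638-652), C30 (806-820) and C36 (974-988) all fall in their own windows. So does every other Day 1 visit that the tables list, from C4 in the tumor tables and from C2 in the laboratory and physical-examination tables. Those last two tables do not list the Cohort 3/4 visits at C13, C16, C19 and C22; that is a separate matter, not counted here.

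**5. Visits after C36.** C42D1 = 1149, C48D1 = 1317, C54D1 = 1485, C60D1 = 1653, C66D1 = 1821 and C72D1 = 1989 are all labelled C36D1. As an illustration, Protocol Section 14.3 plans about 3 years of accrual for Cohort 2. An early subject who stays on study could then reach about 3 x 365.25 + 36 x 28 = 1096 + 1008 = Day 2104. That is past C72D1 but short of C78D1 (Day 2157). Seven scheduled visits would share the C36D1 label, six of them wrongly.

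**6. Which outputs use the labels.**
- Physical-examination findings are tabulated at each visit (SAP 13.5), so they do.
- Any by-visit laboratory or tumor display built on Appendix A would.
- ORR for Cohorts 1 and 2 uses all assessments up to 12 months (12.1.1). The C16D1 window for Cohorts 3 and 4 (380-463, target 421) is correctly placed. PFS and DOR use actual dates (12.2.3, 12.2.4).
- TEAEs are not windowed (13.1), ECOG is a shift to worst score (13.6), and immunoglobulins, cell counts and vital signs use last, minimum and maximum values (13.4.2, 13.4.3, 13.5).

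**7. Minor items, tumor tables only.** C4D1 has no lower limit, so the optional Cohort 3/4 scan in Protocol 6.2.3 ("A repeat CT scan may be performed at Cycle 2, Day 21", that is Day 28 + 21 = 49, +/-3) is labelled C4D1. Nominal months read 0, 1, 1, 1 for the first four visits. In the Cohort 1/2 table these are Days 85, 169, 253 and 309, or 2.8, 5.6, 8.3 and 10.2 months at 30.4375 days per month. The laboratory table gives 2, 5, 8 and 10 for the same days.

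**The case against.** The best defense is that little output depends on these tables. Scheduled visits through C36 that the tables list are labelled correctly, so the misplaced limits matter only for unscheduled or displaced records. The one safety output expressly tabulated at each visit is physical-examination findings. The laboratory section names no by-visit table, although the existence of hematology windows suggests one may be meant. All of this stands, and it limits the point to descriptive output.

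The blank cells may also be deliberate open ends. For C4D1 in the tumor tables that is reasonable: it is the first scheduled on-treatment tumor assessment, baseline is defined separately (SAP 7.2), and the Day 49 scan is optional and not a scheduled response assessment. The laboratory and physical-examination tables do give C4D1 a lower limit (72-99). For C36D1 the defense fails. An open end may be intended, but the label still names a single visit and still pools C42D1 and everything after it.

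A reader might infer that by-visit results in general carry wrong labels, or that late safety trends cannot be read. The documents do not support either. Mislabelling of scheduled visits through these limits begins only after C36, and adverse events and the worst, last, minimum and maximum summaries do not pass through the windows.

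**Conclusion.** The point holds as a minor correction. The certain error is the open C36D1 window: every scheduled visit from C42D1 on takes the C36D1 label, and I found no record-selection rule in the SAP. The second error is two limits set 42 days early, which send off-schedule records in two 41-day bands to the farther visit. No response rate, PFS, DOR or TEAE result changes, and an inference that the efficacy conclusions are affected would be wrong.

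The conclusion assumes 28-day cycles. The figure of six mislabelled visits per subject also rests on the planned accrual time and on a subject who stays on study; the documents give no enrollment dates by subject. The C4D1 lower limit and the nominal months are tidying only, since no assignment rule uses the months.

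**What to change.** In all four tables, end C24D1 at Day 729, set C30D1 to 730-897 and start C36D1 at Day 898. Then do one of the following:
- End C36D1 at Day 1065 and add a window every 168 days (C42D1 1066-1233, and so on). For Cohort 3/4 CT, planned every 12 cycles after C36, end C36D1 at (981 + 1317)/2 = Day 1149, with C48D1 next. Otherwise a CT on Days 1066-1148 would be labelled C42D1, a visit with no planned CT.
- Keep the last window open and relabel it *C36D1 and later*.

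State that the record closest to the target day is used when several fall in one window. If the last window stays open, that rule would generally keep the Cycle 36 record and drop later ones, so the SAP should say whether this is intended.

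In the two tumor tables, correct the nominal months. Keep the optional Cycle 2 Day 21 CT of Cohorts 3 and 4 (Day 49 +/-3) out of C4D1 by giving it its own unscheduled label.

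The cost is an edit to Appendix A and a rerun of by-visit outputs. With separate windows, each late visit will show fewer subjects, because records now pooled under C36D1 will be spread over several visits.

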7.4 Missing Data Handling

No imputation for missing values of efficacy endpoints. Imputation for missing dates such as AE start or end dates and prior and concomitant medication start dates or end dates will be documented in the programming specifications.

8.0 Subject Disposition

Subject disposition will present the number and percentage of subjects in All Treated Population and Efficacy Evaluable Population, who discontinue treatment and reasons, and who do not complete the Safety follow-up as well as the reasons, time on treatment, and time on study.

9.0 Important Protocol deviations

Important protocol deviation (IPD) categories are defined and managed by the study team during the IPD reviews throughout the study before database lock. These definitions of IPD categories, subcategory codes, and descriptions will be used during the course of the study. The final IPD list is used to produce the summary table and by-subject listing for IPDs.

10.0 demographics and baseline disease characteristics

The following variables collected at baseline will be presented:

- Demographics and baseline characteristics
 - Age (years)
 - Descriptive statistics
 - <65 vs. ≥65 years
 - <70 vs. ≥70 years
 - Sex (male, female)
 - Race
 - American Indian/Alaskan Native, African American/Black, Asian, Caucasian/White, Native Hawaiian/Other Pacific Islander or Other
 - Ethnicity (Hispanic or Latino, Non-Hispanic or Latino)
 - Height
 - Weight
 - Region (single site, United States)
 - ECOG performance status
- Baseline disease characteristics
 - Histology
 - For RR, TN
 - CLL
 - SLL

■ PLL

- Time since initial CLL diagnosis to first dose (years)
- Rai stage – Rai stage collected on the electronic case report form (eCRF) and derived Rai stage based on variables collected at screening visit using the criteria described in [Appendix B](#)
- Bulky disease (not applicable for RS/PLL) – defined as if at least one dimension of the lymph node measurement is
 - ≥ 5 cm
 - ≥ 10 cm
- B symptoms – weight loss, fever, night sweats, significant fatigue
- Chromosomal abnormalities
 - del(17)(p13.1) (TP53)
 - del(11)(q22.3) (ATM)
- β 2-microglobulin
 - >3.5 vs. ≤ 3.5 mg/L
 - >3 vs. ≤ 3 mg/L
- Number of prior systemic therapy
 - Descriptive statistics
 - <3 vs. ≥ 3
- Type of prior systemic therapy
- Time since most recent therapy (months)
- Cytopenia
 - Absolute neutrophil count (ANC) $\leq 1.5 \times 10^9/L$
 - Hemoglobin $\leq 11\text{g/dL}$
 - Platelet $\leq 100 \times 10^9/L$
 - Hemoglobin $\leq 11\text{g/dL}$ or platelet $\leq 100 \times 10^9/L$
 - Any of the above
- ANC ($10^9/L$)
- Absolute lymphocyte count (ALC) ($10^9/L$)
- Hemoglobin (g/dL)

- Platelets ($10^9/L$)
- IGHV mutation status (Unmutated IgHV, Mutated IgHV)
- ZAP-70 Methylation Status (Positive, Negative, Not Done/NA)
- Complex Karyotype
 - Subjects with complex karyotype
 - Subjects without complex karyotype

11.0 Medical history

Medical history data will be coded per the Medical Dictionary for Regulatory Activities (MedDRA), summarized by system organ class and preferred term, and presented as a data listing

12.0 Efficacy analyses

Response will be assessed by investigators based on International Workshop on Chronic Lymphocytic Leukemia (IWCLL) Response Assessment Criteria (modified from Hallek 2008) with incorporation of the clarification for treatment-related lymphocytosis per Cheson 2012 for CLL/SLL.

The efficacy analysis will be performed using All Treated Population. The Efficacy Evaluable Population will be used for primary efficacy analysis.

12.1 Primary Efficacy Endpoint and Analysis

12.1.1 Overall Response Rate (ORR)

ORR is the proportion of subjects who achieve complete remission (CR), CR with incomplete bone marrow recovery (CRI), nodular partial remission(nPR), or partial remission (PR) while on treatment before the initiation of new anticancer therapy or stem cell transplant.

For Cohorts 1 and 2, the ORR(PR or better) at the all available response assessments up to the 12-months will be calculated and 95% exact binomial CIs will be provided.

ORR will be summarized using All Treated Population and Efficacy Evaluable Population.

For CLL disease subgroups, ORR, including PRL as a response, (only for Cohorts 1 and 2), will also be summarized in the same fashion.

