8.4 Discontinuation Follow-up

After discontinuation of study treatment for any reason (except for death, lost to follow up, or withdrawal of consent), each subject should be followed until disease progression. If disease progression has not occurred at the time of the 30-day SFU visit, discontinuation follow-up visits should occur approximately every 12 weeks until disease progression. During this period, subjects will be followed via CT scans (every 24 weeks), CBC with differential, physical examinations (including vital signs and weight), serum chemistry, peripheral blood MRD (every 6 months for subjects in Cohorts 3 and 4 who will be monitored while off study drugs), and bone marrow biopsy and aspirate (as clinically indicated); after 2 years in discontinuation follow-up, CT scans will be yearly. Refer to the Schedule of Assessments ([Section 8](#)) for a full list of assessments required during this period.

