14.1 Study Overview

This is a Phase 1b study with expansion to evaluate the safety and preliminary efficacy of acalabrutinib in combination with obinutuzumab, or with venetoclax and an anti-CD20 antibody (rituximab or obinutuzumab) in 4 separate cohorts of subjects: those with relapsed/refractory CLL (Cohorts 1 and 3) and those with treatment-naive CLL (Cohorts 2 and 4). Enrollment will begin in Cohort 1, where the recommended dose will be based on decision rules from a standard 3+3 Phase 1 trial design and will proceed as outlined in [Figure 4](#). Both Cohorts 1 and 2 will be expanded to better evaluate the toxicity profile of these combination regimens, and also to detect moderate to large increases in ORR at 12 months relative to historical control. Cohorts 3 and 4 will be enrolled to establish the safety profile of the combination of acalabrutinib plus venetoclax plus an anti-CD20 antibody. The ORR will be defined as the proportion of treated subjects who achieve complete or partial remission at Cycle 16 for Cohorts 3 and 4. The cumulative ORR over time will be summarized for each of the 4 cohorts individually.

Figure 4: Trial Design

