14.6 Analysis Plan

14.6.1 Primary Endpoints

For Cohorts 1 and 2, the ORR (PR or better) at the 12-month response assessment will be calculated and 95% exact binomial CIs will be provided. For Cohorts 1 to 4, toxicities will be tabulated by type and grade using NCI-CTCAE version 4.03 criteria or higher and displayed in summary form. In addition, the number of subjects requiring dose reductions, and the reason for going off each treatment may be summarized.

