12.2.1 Overall Response Rate(ORR)

The ORR of the combination therapy of acalabrutinib plus venetoclax plus an anti-CD20 antibody at Cycle 16 (Cohorts 3 and 4) will be calculated and 95% exact binomial CIs will be provided

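### SAP 12.1.1 counts a response only while on treatment, a condition absent from the protocol's ORR, so first responses documented after stopping are lost and, on one reading, so are off-drug remissions at Cycle 16

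*SAP*

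**What the plan says.** **SAP 12.1.1** defines ORR as the proportion reaching CR, CRi, nPR or PR "while on treatment before the initiation of new anticancer therapy or stem cell transplant". For Cohorts 1 and 2 it adds that ORR "at the all available response assessments up to the 12-months will be calculated".

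**SAP 12.2.1** gives no definition of its own for Cohorts 3 and 4. It says only that the ORR "at Cycle 16 (Cohorts 3 and 4) will be calculated and 95% exact binomial CIs will be provided". SAP 12.2.2 likewise gives the CR rate without a definition.

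**Protocol 14.1** defines ORR for Cohorts 3 and 4 as "the proportion of treated subjects who achieve complete or partial remission at Cycle 16 for Cohorts 3 and 4". **Protocol 14.6.1** says: "For Cohorts 1 and 2, the ORR (PR or better) at the 12-month response assessment will be calculated". Neither requires the subject to be on study drug.

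**Protocol 8.4** says that after treatment stops "each subject should be followed until disease progression", with visits about every 12 weeks and CT every 24 weeks. It excepts death, loss to follow-up and withdrawn consent. As extracted, Protocol Tables 12 and 13 place an overall response assessment in both the safety follow-up and the discontinuation follow-up columns.

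**SAP 12.2.4 and 12.2.5** start duration of response at the first CR, CRi, nPR or PR, and measure time to response to the first PR or better. Neither has an on-treatment condition.

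**The concern.** The SAP narrows the protocol's endpoint and gives no reason. The protocol asks whether a treated subject is in remission at a stated time. The SAP asks whether remission was reached before study drug stopped, which mixes tolerability into the response rate.

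Late documentation is plausible. Protocol section 9 requires CR and PR to hold for at least 2 months. In Cohorts 3 and 4 the marrow check follows a negative blood MRD result by 2 to 3 months (Tables 12 and 13, footnote G). A subject who improves on drug and then stops for toxicity may have the response recorded only after the last dose. That subject would have a time to response and a duration of response, yet be a non-responder for ORR.

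The condition is also undefined for these regimens. Protocol 7.1.3.3 and 7.2.2.1 let one drug stop while others continue, and SAP 12.1.1 does not say which last dose ends treatment. Two programmers could derive different rates from the same data.

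**Working it through.** **1. The plan's own design figures.** Inputs are from Protocol 14.4: null 50%; alternatives 75% (relapsed/refractory) and 80% (treatment-naive); promising if at least 17 of 26 or at least 13 of 19 respond. Alternatives are matched by disease setting, because the cohort labels in that sentence are swapped. Exact binomial:

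- Cohort 1: P(X ≥ 17 | 26, 0.50) = 0.084; P(X ≥ 17 | 26, 0.75) = 0.909.
- Cohort 2: P(X ≥ 13 | 19, 0.50) = 0.084; P(X ≥ 13 | 19, 0.80) = 0.932.

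The stated 0.10 alpha and 90% power are met. Removing the condition changes none of these figures.

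**2. Who is lost under the SAP text.**

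| Subject | Cohorts 1–2 (any assessment up to 12 months) | Cohorts 3–4, status at Cycle 16 | Cohorts 3–4, achieved by Cycle 16 |
|---|---|---|---|
| Response on treatment, then off all drugs, still in remission | counts | **lost** | counts |
| First PR or better after the last dose | **lost** | **lost** | **lost** |
| One drug stopped, another continuing | not defined | not defined | not defined |

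The last two columns assume that 12.1.1 carries into 12.2.1. Response-based stopping of acalabrutinib in Cohorts 3 and 4 is allowed only after Cycle 24 (Tables 12 and 13, footnote A), so it cannot affect Cycle 16. In Cohorts 1 and 2, a subject who stops after an MRD-negative CR reached on treatment remains a responder.

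**3. Size per subject.**

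- n = 12: 1/12 = 8.3 points
- n = 19: 1/19 = 5.3 points
- n = 26: 1/26 = 3.8 points

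As an illustration at n = 12 with exact 95% intervals: 12/12 gives 73.5% to 100%, 11/12 = 91.7% gives 61.5% to 99.8%, and 10/12 = 83.3% gives 51.6% to 97.9%.

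At the margin, one rescored subject takes 17/26 to 16/26, or 13/19 to 12/19, which crosses the plan's not-promising line.

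**4. Sensitivity of the design.** Let d be the share of true responders lost to the condition. The documents do not give d, so the range is an assumption. Power is recomputed with the alternative multiplied by (1 − d); for d = 5% these are 0.75 × 0.95 = 0.7125 and 0.80 × 0.95 = 0.76.

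| d (assumed) | Cohort 1 | Cohort 2 |
|---|---|---|
| 0% | 0.909 | 0.932 |
| 2% | 0.875 | 0.905 |
| 5% | 0.812 | 0.851 |
| 10% | 0.677 | 0.734 |

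This isolates the on-treatment condition. It leaves out the opposite effect of the SAP's cumulative 12-month rule.

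**5. Data available off treatment.** The Cycle 16 window in SAP Appendix A runs from day 380 to day 463, which is 463 − 380 + 1 = 84 days, or 12 weeks. Off-treatment CT is every 24 weeks, so some subjects may have no CT inside the window.

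**The case against.** An on-treatment response rate is a legitimate quantity. SAP 7.1 plans no formal tests, and the Cycle 16 ORR is a secondary, descriptive estimate in 12 subjects per cohort. All of that is true. It limits the consequence but does not explain why the SAP departs from the protocol.

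Four stronger readings are tempting, and the documents do not support them.

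- **A reader might infer that anyone who stops early and is in remission at 12 months is scored a failure.** SAP 12.1.1 counts every assessment up to 12 months, so a response reached on treatment survives the stop.
- **A reader might infer that the SAP's ORR is biased downward overall.** The condition alone can only remove responses. But the SAP also counts a Cohort 1 or 2 subject who responds early and progresses before 12 months, whom the protocol's 12-month assessment would not count. The net direction there is unknown.
- **A reader might infer that stopping acalabrutinib alone makes a subject a non-responder.** A subject still receiving venetoclax or antibody is still receiving study treatment, and Protocol 8.3 times safety follow-up from the last dose of all study drugs. The cycles at which the antibody and venetoclax end are redacted, so what remains at Cycle 16 cannot be read.
- **A reader might forecast a Cycle 16 shortfall of one or two subjects in 12 (8.3 or 16.7 points).** That needs an early-stopping rate the documents do not give, every such subject in remission, and none credited with an earlier on-treatment response.

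**Conclusion.** The mismatch is real. SAP 12.1.1 carries a condition that is absent from the protocol's ORR and from the SAP's own duration-of-response and time-to-response definitions, while off-treatment response data are scheduled.

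In Cohorts 1 and 2 only first responses documented after stopping are lost. In Cohorts 3 and 4 the loss is equally narrow if Cycle 16 ORR means achieved by then. It extends to every subject in remission but off all study drugs if 12.1.1 carries into 12.2.1 and status at the visit is meant. The SAP does not say which.

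The size is known per subject only (step 3 of the working). The total is not, and the power figures rest on an assumed share. Because no formal test is planned, the effect falls on the reported ORR, its interval and the informal promising rule. The change is worth making because it brings the endpoint back to the protocol at almost no cost.

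**What to change.** 1. In SAP 12.1.1 delete the words *while on treatment*. Count a response documented before progression, new anticancer therapy or transplant, whether or not study drug continues.
2. Keep the protocol's time anchors: the 12-month assessment for Cohorts 1 and 2, and Cycle 16 for Cohorts 3 and 4. Make this change together with the first. Restoring a point-in-time anchor while leaving the condition in place would extend the loss in Cohorts 1 and 2 to subjects in remission off drug.
3. State whether Cycle 16 ORR is status at that visit or response achieved by then.
4. Apply the same definition in SAP 12.2.1 and 12.2.2.
5. Show the on-treatment rate as a sensitivity row, with on treatment defined as up to the last dose of any study drug.

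The cost is a short wording change and one extra derivation flag. The limitation is that off-treatment CTs are sparser, so some subjects may lack a CT in the Cycle 16 window. Report how many. The new-therapy and transplant condition is also absent from the protocol's ORR; if it is kept, the SAP should say so openly.
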